4) State the specific research hypotheses or questions to be addressed in this study	
The goal of this study is to examine the effects of maternal interpretation biases on child interpretation biases and child anxiety symptoms during an anxiety-provoking speech task. We are proposing to address these objectives using a sample of 130 children with anxiety disorders and their clinically anxious mothers. Specific aims are as follows: Specific Aim 1: To test the effects of positive interpretation bias training on maternal anxious behavior. 1.1: Clinically anxious mothers who are trained to interpret child-related ambiguous situations in a positive manner will exhibit reduced anxious behavior as rated by objective observers relative to clinically anxious mothers who do not receive interpretation bias training. Specific Aim 2: To test the effects of positive interpretation bias training on children's and mothers' perceptions of threat to an anxiety-provoking speech task. 2.1: Mothers trained to interpret child-related ambiguous situations in a positive manner will rate the speech task as less threatening than mothers who do not receive interpretation bias training. 2.2: Children of clinically anxious mothers who are trained to interpret child-related ambiguous situations in a positive manner will rate the speech task as less threatening than children of clinically anxious mothers who do not receive interpretation bias training. Specific Aim 3: To test the effects of positive interpretation bias training on children's anxious behavior, physiology, and performance during an anxiety-provoking speech task. 3.1: Children of clinically anxious mothers who receive positive interpretation bias training (vs. those who do not receive such training) will exhibit lower anxiety during the speech task, as evidenced by (a) lower observer-rated anxious behavior, (b) increased heart rate variability, and (c) better observer-rated performance during the speech task.

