25) Where, how long, and in what format (such as paper, digital or electronic media, video, audio or photographic) will data be kept? In addition, describe what security provisions will be taken to protect these data (password protection, encryption, etc.). [Note: University of Houston policy on data retention requires that research data be maintained for a minimum of 3 years after completion of the project. All research data collected during this project is subject to the University of Houston data retention policy found at http://www.research.uh.edu/Home/Division-of-Research/Research-Services/Research-Policies/Access-to-and-Retention-of-Research-Data.aspx]	Subject confidentiality will be protected to the full extent required by law and applicable local, State and Federal regulations and guidelines. All paper-format data will be kept in locked files in the locked office (HBSB Room 475) of the project coordinator and accessible only to study staff, governmental agencies (e.g., NIH) and local convening authorities (e.g., UH IRB) for the purpose of audit regarding scientific validity and/or aspects pertaining to the ethical conduct of human clinical investigation. Electronic data will be kept in password-protected files and kept on the University's secure servers which meet all applicable federal and state standards for data privacy and protection. Upon completion of the study, data encryption procedures will be used to safeguard all files. Files will be kept for 7 years after study completion.

Analyses 1.1: Related to H1, scores on coding dimensions of maternal anxious behavior will be checked first for potential reduction or combination due to low frequency (i.e., not all codable behaviors are actually observed). If child sex effects on maternal behaviors are observed, child sex will be included as a covariate. Then, a two-group (positive training vs. neutral training), one-way MANOVA (5 DVs: manifest anxiety, passivity, promotion of avoidance, overprotection, and intrusiveness) will be used to examine the effects of the positive interpretation bias training paradigm on maternal anxious behavior during the parent-child discussion. If the MANOVA is significant, ANOVAs for each significant dependent variable will be conducted, controlling for Type I error using Holm's (1979) modified Bonferroni correction method (Jaccard & Guilamo-Ramos, 2002).

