Analyses 2.1: Related to H2 and H3, Holm's (1979) modified Bonferroni-corrected independent-samples t-tests will examine mean group differences (positive training vs. neutral training) in child and maternal ratings of perceived threat prior to the anxiety-provoking speech task.

Analyses 3.1: Related to H4.1, coding of child anxious behavior will be first subjected to similar procedures described for H1 above. A two-group (positive training vs. neutral training) one-way MANOVA (4 DVs: facial expression, body movements, speech quality, and content) will be used to examine the effects of the positive interpretation bias training paradigm on child behavior during the parent-child discussion. If the MANOVA is significant, the follow-up procedures will be identical to those reported above (see Analyses 1.1.). To address H4.2, ANCOVAs (controlling for baseline RSA) will be used to examine between group (positive training vs. neutral training) mean differences in children's RSA. Finally, we will conduct independent-samples t-tests to examine mean group differences in overall observer-rated performance during the speech (H4.3).

Analyses 4.1: Related to H5, a hierarchical linear regression will be conducted using child anxiety during the speech task as dependent variable in order to examine child SoP diagnosis as a moderator of associations between maternal interpretation biases child anxiety symptoms. Predictor variables will be mean-centered. In the first step of the model, any necessary control variables will be entered. In the second step, both maternal interpretation biases and child SoP diagnosis will enter the model as predictor variables. In the third step, a maternal interpretation biases X child SoP interaction term will enter the model as a predictor.

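### Aim 3.1(a) concerns child anxious behaviour during the speech, but the only between-arm test of that behaviour is set in the mother-child discussion before the speech

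*Combined protocol and SAP*

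**What the plan says.** Item 4 sets the whole of Specific Aim 3 in one window: children's "anxious behavior, physiology, and performance during an anxiety-provoking speech task". Hypothesis 3.1 repeats it. Children of trained mothers "will exhibit lower anxiety during the speech task, as evidenced by (a) lower observer-rated anxious behavior", with the other two indicators being "b) increased heart rate variability, and (c) better observer-rated performance during the speech task".

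Item 11 gives the order of events. Mother and child discuss how to approach the speech, and the mother's behaviour in that discussion is coded. The speech follows, and the child's anxiety, heart rate and performance are assessed on it. Item 12 adds that the speech is given to a recording video camera.

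Analyses 3.1 opens: "Related to H4.1, coding of child anxious behavior will be first subjected to similar procedures described for H1 above". It then specifies a two-group one-way MANOVA ("4 DVs: facial expression, body movements, speech quality, and content"), which "will be used to examine the effects of the positive interpretation bias training paradigm on child behavior during the parent-child discussion". The same paragraph gives an ANCOVA on RSA for H4.2, and t-tests for "mean group differences in overall observer-rated performance during the speech (H4.3").

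**The concern.** The hypothesis names the speech. The analysis that appears to test it names the discussion that precedes the speech. These are different situations: in one the child is talking with the mother, in the other the child is speaking to a camera. A difference between arms in one is not evidence of a difference in the other.

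If the analysis sentence is followed literally, the H4.1 result describes behaviour in the discussion, could be reported as the answer to 3.1(a), and leaves the predicted effect on behaviour during the speech untested. If the mismatch is noticed only once the data are in hand, two written texts support two different windows, and the choice between them is open to challenge.

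**Working it through.** No sample size, power or error-rate figure is involved, so there is nothing numerical to reproduce. The check sets each between-arm analysis against the window that the aims and design give for its outcome.

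| Analysis | Outcome | Window in the analysis text | Window in items 4 and 11 | Agree? |
|---|---|---|---|---|
| 1.1 (H1) | Maternal anxious behaviour | Discussion | Discussion (item 11) | Yes |
| 2.1 (H2/H3) | Maternal threat rating | Before the speech | After the discussion, before the speech assessments (item 11) | Yes |
| 2.1 (H2/H3) | Child threat rating | Before the speech | As above | Yes |
| 3.1 (H4.1) | Coded child anxious behaviour | Discussion | Speech (item 4) | **No** |
| 3.1 (H4.2) | Child RSA | Not stated | Speech (item 4) | No conflict |
| 3.1 (H4.3) | Overall performance | Speech | Speech (item 4) | Yes |

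One of the six outcome sets conflicts.

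**Does H4.1 correspond to 3.1(a)?** The document does not define H1 to H5, so the link is inferred. H4.1, H4.2 and H4.3 cover anxious behaviour, RSA and performance. Hypothesis 3.1(a), (b) and (c) cover anxious behaviour, heart rate variability and performance, in the same order. If the inference were wrong, the position would be no better: 3.1(a) would still have no test, and the child-discussion outcome would match no stated aim.

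**Does another analysis cover 3.1(a)?** Analyses 4.1 (H5) takes child anxiety during the speech as its outcome. Its named predictors are maternal interpretation biases, the child's SoP diagnosis and their interaction, plus unspecified control variables. Arm is not named, and the outcome is not identified as the coded behaviour, so it is not a between-arm test of 3.1(a). H4.3 is overall performance, which Hypothesis 3.1 lists separately as (c).

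**Count.** Between-arm tests of coded child anxious behaviour in the discussion: 1 MANOVA + up to 4 follow-up ANOVAs = up to 5, or fewer if variables are combined or the MANOVA is not significant. In the speech: 0. Parts of Hypothesis 3.1 with a fitting between-arm test: (b) and (c), so 2 of 3.

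**Where the phrase may come from.** Analyses 1.1 examines the effect of the "positive interpretation bias training paradigm on maternal anxious behavior during the parent-child discussion". The H4.1 sentence borrows the H1 procedures and ends in the same words. Two of the four child variables, speech quality and content, fit a speech naturally. A carry-over is the likeliest explanation, though the document does not establish it.

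**The case against.** The strongest reply is that this is an evident drafting slip which the study team would resolve correctly. The aim, the description of what is assessed on the speech, the choice of variables and the setting of H4.3 all point to the speech. The speech window is also already written in item 4, so aligning the analysis with it would follow a prior hypothesis and would not be a free choice after the fact. That largely stands: literal misanalysis is a risk, not the expected outcome, and the loss of pre-specification is partial. What remains is that the sentence is operative, grammatical and executable, and that a coder or analyst working from the analysis section alone would use the discussion.

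A second reply is that item 11 does not exclude coding the child in the discussion; it mentions only the mother. That is right. Item 11 is silent on the point, and the firm contradiction is with item 4. The same silence means that the document describes no child codes from the discussion, which makes a literal run somewhat less likely.

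Third, the instruments are described in attachments (item 15) that are not part of this document, and H5 has no counterpart in item 4, so the analysis text may follow a hypothesis list found elsewhere. Either source could state the intended window. That limits the finding to the text at hand, but it does not remove the disagreement between two statements that are both present.

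**Conclusion.** The concern holds. Within this document, Hypothesis 3.1(a) has no between-arm test in the window it names, and the one between-arm test of coded child anxious behaviour is set in an earlier window. The effect is confined to one of three parts of Hypothesis 3.1 and one of six between-arm outcome sets, but it is the only behavioural-anxiety part of the child hypothesis.

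Reading H4.1 as the test of 3.1(a) rests on matching order and content. The finding that the document plans no between-arm test of coded anxious behaviour during the speech does not depend on that reading. The text has to be settled before analysis, because following it as written would leave a stated hypothesis untested.

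**What to change.** Reconcile item 4 and Analyses 3.1 before outcome data are examined.

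- **If the speech was intended:** in the H4.1 sentence, replace the reference to the discussion with the speech task for all four child variables. List any analysis of child behaviour in the discussion separately, as secondary.
- **If the discussion was intended:** state that outcome in the aims, and add a between-arm MANOVA of the same four variables during the speech, with the same follow-up rule, as the test of 3.1(a).
- **In either case:** define H4.1 in the analysis text or tie it explicitly to Hypothesis 3.1(a).

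The first route costs one phrase. The second costs one MANOVA with its follow-ups, one sentence in the aims, and coder time for a second window. Neither needs new data collection for the speech, which is already given in front of a video camera (item 12) and already has to be rated by observers for H4.3.

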11) Describe the research study design. (Describe the research methods to be employed and the variables to be studied. Include a description of the data collection techniques and/or the statistical methods to be employed.)	
The study involves two sessions on separate days. All sessions take place at the University of Houston. All parent-child dyads will complete multi-method assessments of interpretation biases and anxiety disorder symptoms (and other forms of psychopathology). Clinically anxious mothers of children with anxiety disorders will be randomly assigned to either a computerized training paradigm that teaches them to interpret child-related ambiguous situations in a positive manner (n=65; "positive training" condition) or a neutral condition that does not train interpretation of such situations in either a positive or negative direction (n=65; "neutral" condition). Specifically, in the "positive training" condition, a child-related scenario will be presented on the computer screen (e.g. meet the teacher day). Two possible interpretations of the event are subsequently presented on the screen: a threatening and a non-threatening interpretation. Mothers will be asked to choose the most accurate interpretation of the event by pressing on the corresponding key on the keypad. Mothers will receive positive feedback and a brief explanation when they choose the positive interpretation explanation, and negative feedback and a brief explanation when they choose the negative interpretation explanation. Mothers randomly assigned to the neutral condition will not receive any feedback on their answers. Children will subsequently be asked to participate in an anxiety-provoking speech task. Prior to this task, they will have the opportunity to discuss how they will approach the task with their mother, and their mothers' behavior during this interaction will be coded. Following the discussion, children and mothers will be asked how threatening they perceive the task to be and will complete a second computerized assessment of interpretation biases to assess interpretation biases post-training. Finally, children's anxiety, heart rate, and performance on the task will be assessed.

	This study involves two sessions on separate days. During the first session, mothers and children will complete several paper and pencil questionnaires (attached) that ask questions about the child's thoughts, feelings, and

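### Analyses 4.1 (H5) names no training-arm term and does not say which maternal bias score it uses; with the post-training score, the bias slope, and in some cases the bias-by-SoP term, can absorb the randomised training effect.

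*Combined protocol and SAP*

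**What the plan says.** Analyses 4.1 states that "a hierarchical linear regression will be conducted using child anxiety during the speech task as dependent variable". The steps are:

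- Step 1: "In the first step of the model, any necessary control variables will be entered". The controls are not listed, so arm is neither named nor excluded.
- Step 2: "In the second step, both maternal interpretation biases and child SoP diagnosis will enter the model as predictor variables".
- Step 3: "In the third step, a maternal interpretation biases X child SoP interaction term will enter the model as a predictor".

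No arm term or arm interaction appears, and the analysis is not limited to one arm. Analyses 1.1 to 3.1, by contrast, all name the positive-versus-neutral comparison.

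Item 11 (study design) randomises mothers 65 to 65. The active arm receives a "computerized training paradigm that teaches them to interpret child-related ambiguous situations in a positive manner". Items 11, 12 and 14 show that maternal bias is measured both before and after training. Analyses 4.1 does not say which score enters the model.

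Items 11 and 12 also differ on when the post-training task takes place. Item 11 puts it after the mother-child discussion, and item 12 puts it directly after training, before the discussion.

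**The concern.** The H5 predictor is the construct that the trial sets out to change in half the mothers, and the outcome is measured after that change, in the same session. Specific Aim 3 (item 4) expects children of trained mothers to show lower anxiety. If the post-training score is used, the arms may therefore differ on both predictor and outcome. A regression that ignores arm would then credit to maternal bias any part of the training effect that the bias score does not carry.

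At stake is the reading of H5. A significant bias slope, or an apparent moderation by SoP, could appear although bias has no relation to child anxiety within either arm. Item 5 gives as the study's significance a specific link between change in maternal cognition and child responses, and a pooled slope without arm is weak evidence for that.

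**Working it through.** The documents give no alpha, effect size, SD or SoP prevalence for H5, so there is no planned figure to reproduce. The arm sizes agree: 65 + 65 = 130.

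**Inputs.** From the documents: 130 dyads, 1:1 allocation, and the H5 model terms. Assumed: two-sided 5% level; 50% of children with SoP; training lowers the bias score by d SD; training changes child anxiety by c SD through routes that the bias score does not carry; true within-arm bias slope and bias x SoP interaction both 0.

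**Formula, post-training score, arm omitted.** Arm has variance 1/4, so within an SoP group cov(arm, bias) = -d/4 and var(bias) = 1 + d²/4. Therefore

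pooled slope = within-arm slope + c × k(d), where k(d) = -(d/4) / (1 + d²/4).

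For d = 1, k = -0.25/1.25 = -0.20.

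- Slope with c = -0.5 in both SoP groups: (-0.5)(-0.20) = 0.10, when the truth is 0.
- Interaction with equal effects: 0.10 - 0.10 = 0.
- Interaction with effects of 0.8 SD (SoP) and 0.2 SD (no SoP): 0.16 - 0.04 = 0.12.
- Interaction with effects of 1.0 SD and 0 SD: 0.20 - 0 = 0.20.
- Interaction with c = -0.5 in both groups but bias shifts of 1.0 SD (SoP) and 0.4 SD (no SoP): k(0.4) = -0.10/1.04 = -0.096, so 0.100 - 0.048 = 0.052.

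**False-positive rates by simulation** (least squares, n = 130, several thousand replicates per setting, post-training score, d = 1):

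| Training effect, SoP / no SoP | Term | No arm term | Arm and arm x SoP |
|---|---|---|---|
| 0.5 / 0.5 SD | bias slope | about 22% | about 5% |
| 0.5 / 0.5 SD | bias x SoP | about 5% | about 5% |
| 0.8 / 0.2 SD | bias x SoP | about 11% | about 5% |
| 1.0 / 0 SD | bias x SoP | about 23% | about 5% |

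Over bias shifts of 0.5, 1 and 1.5 SD, the slope figure at a 0.5 SD training effect is about 10%, 23% and 39%. The interaction figure is about 7%, 11% and 15% at 0.8/0.2 SD, and 10%, 22% and 38% at 1.0/0 SD. Repeat runs agree within about two percentage points.

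**Does an arm main effect suffice?** At d = 0.8 with training effects of 0.8/0 SD, the interaction is falsely significant in 12% without arm, 12.5% with an arm main effect only, and 5% with arm and arm x SoP. An arm main effect repairs the slope (19% to 5.5% at d = 0.8, c = -0.5). It does not repair the interaction when the training effect differs by SoP. Where only the bias shift differs (0.4 versus 1.0 SD), the interaction figure is 6% without arm and 5% with it.

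**Pre-training score.** It is independent of arm by randomisation. With training effects of 0.8/0 SD, the slope and the interaction both stay at about 0.00 with 5% false positives, with or without arm. Power is a separate matter. Assume a true interaction of 0.8 in the neutral arm:

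- Training leaves the link intact: pooled interaction 0.80, power 99%.
- Training halves the link: 0.60, about 90%.
- Training abolishes the link: 0.40, about 56%.

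**The case against.** The strongest defence is that the plan never selects the manipulated score. A pre-training score is available, and with it the pooled model produces no false positives from the training effect. Step 1 is also open enough to admit arm. H5 speaks of moderation of associations, so it is not presented as a randomised effect. It is not among Specific Aims 1 to 3, and Analyses 1.1 to 3.1 are untouched.

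Much of this stands, and it limits the point. Three stronger readings are tempting, but the documents do not support them:

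- *A reader might infer that the H5 interaction is necessarily contaminated.* It is not. That needs a post-training score and a training effect or bias shift that differs by SoP. With both equal, the interaction stays near 5% and only the slope is affected. If the bias score carries the whole training effect (c = 0), the formula gives no distortion at all.
- *A reader might infer that a pre-training score would dilute the interaction in any case.* A uniform training shift leaves the pre-training slope unchanged. Dilution requires training to weaken the link, and nothing in the documents says that it does.
- *A reader might infer that adding arm x bias would recover the moderation in the neutral arm.* In the abolished-link case the pooled interaction remains 0.40, with power about 56%, with or without that term.

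The defence does not remove the gap. The time point is unstated, and an arm main effect admitted as a control would not protect the interaction, which is the H5 test.

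**Conclusion.** The point holds as a conditional one. As written, the H5 model can be fitted with a post-training score and no arm term, and in that form it can mislead. In the settings tried, with a 1 SD bias shift, the slope is falsely significant in about 22% of trials at a 0.5 SD training effect. The interaction ranges from about 5% (equal training effects) through 11% (0.8/0.2 SD) to 23% (1.0/0 SD), against 5% nominal. The last of these is an extreme case.

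All the rates rest on assumed effect sizes, an assumed 50% SoP prevalence, and a training effect not carried by the bias score. They show what the omission could do, not what it will do. If the pre-training score is intended, the false-positive problem disappears and what remains is a missing specification. The matter merits a change to the analysis text, in proportion to H5's place outside the three stated aims.

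**What to change.** In Analyses 4.1:

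1. State whether the pre- or post-training maternal bias score is the predictor, and reconcile items 11 and 12 on when the post-training task takes place.
2. Enter training arm in step 1, and arm x SoP together with bias x SoP in step 3.
3. Describe the bias-based slopes as observational. Arm x SoP can also be reported as the randomised test of whether the training effect differs by SoP.

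Optional: if moderation undisturbed by training is of interest, add arm x bias x SoP (with its lower-order terms) or a neutral-arm-only sensitivity analysis. Either costs power. With the link intact and a true interaction of 0.8, the three-way model lowers power from 99% to roughly 85%.

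The cost of items 1 to 3 is a change of wording and two model terms (arm and arm x SoP), so two degrees of freedom out of 130. No new data are needed: arm, SoP diagnosis and both bias scores are already part of the planned data.
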